### 4.2 Baseline Analysis Set

The *Baseline Analysis Set* (BAS) consists of all patients of the APS and patients:

- where baseline signature has been taken (signed eCRF)
- with AF who are scheduled for Phased RFA
- that meet all remaining eligibility criteria
- provide any further documentation at baseline
- a phased RFA procedure was started - procedure form was fulfilled at least: date of the procedure, PVAC GOLD catheter used (opened), number of PV applications > 0
- patient did not exit the study prematurely for the reason: Patient were enrolled, but Phased RFA procedure was not started

According to the Appendix B, the BAS will be used for the interim and final analysis as well as for post-hoc analysis. The final analysis includes the additional objective (SAP chapter 8.2) and ancillary objectives (SAP chapter 8.3), where the BAS will be applied.

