Describe single catheter PVAC GOLD utilization in persistent AF

Rational: Ablation of persistent AF is a challenging and long procedure with varying success rates (7). There is a significant variety of AF forms covered by the definition “persistent AF”. According to current European guidelines persistent AF is defined as AF that persists without interruption for 7 days or longer. Whenever patients have been cardioverted during the first 7 days of an AF episode should be classified as persistent one. A single CV later than 48 hours from arrhythmia onset turns a patient with paroxysmal AF into a persistent one and has to be distinguished from the patient with AF episodes for weeks or months which never terminate spontaneously. Above the limited clinical ability to discriminate paroxysmal and persistent AF, the success rate of ablation for persistent AF can vary significantly, which may be due to large structural and electrical remodeling that occurs in the LA between early persistent AF and long-standing persistent AF (28). The Phased RFA meta-analysis reported 54.1% chronic success among persistent AF patients (19). It was shown that utilization of MASC and MAAC catheters for complex fractionated atrial electrograms additionally to PVI lead to 66% long-term success rate in persistent (14) and 49% in longstanding persistent AF (29), respectively. However, recent results from the STAR AF II study have shown that additional linear or focal lesions do not improve efficacy compared to PVI alone (8). The maintenance of sinus rhythm is not dramatically different between ‘persistent’ AF patients undergoing PVI alone compared with patients undergoing more extensive ablation approaches, including a risk to develop left atrial tachycardia. Until now it is not possible to tailor precisely an ablation strategy to persistent and longstanding persistent AF. It is a point of interest for the registry to evaluate which tools and consumables participating centers use in persistent and long standing persistent AF and to verify patients' characteristics, procedure approaches and estimates mid-term outcome across participating sites.

Endpoint definition:

- Describe % of patients with persistent vs paroxysmal as an indication for Phased RFA at baseline
- Describe if additional substrate modification (liner lesions, CAFÉ ablation) were performed above PVI

Analysis Methods: respective subgroup analysis can be considered for patients:

- With persistent versus paroxysmal AF.

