The "Procedure" CRF will be used to collect data about the ablation procedure and discharge from the medical center. Information regarding anticoagulation therapy, procedure summary information, sedation and consumables, PVI confirmation, cardiovascular medication, date and status at hospital discharge is to be collected. Verification of study defined AEs will be done during the procedure and at the moment of hospital discharge.

If the attempt to conduct Phased RFA ("index" procedure) is not successful for clinical or technical reason, patients will stay enrolled into the registry. If Phased RFA is repeated ("repeated" procedure) or re-do due

to arrhythmia recurrence, the “procedure” CRF should be filled in. Information about all Phased RFA attempts will be used for the analysis. If patient has re-do procedures with some other technology than Phased RFA, Procedure CRF is not required; information about technology which was used for re-ablation to be collected in eCRF “General FU”.

During the Phased RFA, the investigator may require use of other commercially available devices for other ablations such as Afi/LAT or other AF triggers. The use of other devices will be at the investigator’s discretion and use will be documented on the eCRF.

Hospital discharge needs to be completed when the patient is discharged from the hospital, this data to be collected as a part of the procedure visit. Information about date of discharge, reportable adverse event since the procedure and recommended medication information is to be collected. Post-ablation drug regimen is determined at clinical discretion of the treating investigator.

General Follow up visits (in hospital)

The “General” FU CRF will be used to collect data during all standard visits at the site within the following 12 months after the index or study procedure. Data to be collected include: arrhythmia assessment, diagnostics, symptoms, hospitalizations, ablation information and medication. If “General FU” will take place due to system/procedure related AE, “Adverse Event” CRF should be filled in additionally to the “General” FU CRF.

If at any moment during FU, the patient withdraws PIC/PDRF or PI receives information about the patient’s death, the “Exit” CRF should be filled in addition to the “General FU” CRF. All data collected prior to the patient exit will be used for analysis, unless different is required by local laws and regulations.

12 months FU (in hospital or by phone)

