### 4.3 Full Analysis Set

The *Full Analysis Set* (FAS) consists of all patients of the BAS and thereof patients with a valid 12MFU form of 12 months visit or 12 months telephone interview. The rules for valid 12MFU form are described in the chapter 7.2.3.

A documented 12MFU form includes at least:

- Date of the visit/FU and
- Vital status and
- Signed eCRF 12MFU visit or 12MFU by phone form

The FAS will be used to analyse the main objective (SAP chapter 8.1), additional objective (SAP chapter 8.2) and ancillary objectives (SAP chapter 8.3). The FAS will be analysed at the end of this study.

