## 8.2 Statistical analyses for additional objective

### 8.2.1 Estimate Phased RFA procedure safety

Major procedure related complications include vascular complications secondary to venous access, cardiac tamponade, embolic stroke, esophageal injury, phrenic nerve injury, PV stenosis, reentrant tachycardia arrhythmias arising from ablations, mainly left Afl.

Adverse events (AE) including their relatedness to the respective procedure, are documented starting from the first documented procedure until the 12 month FU. For this analysis only adjudicated AE data (SUO form) and coded AE data (from free text fields) will be used. In addition, TIA/Stroke events will be taken from general FU forms to calculate procedure safety. Analysis will be performed at 30 days and at 12 months after procedure.

If no adverse event was documented within the 12 month FU period, the patient or the procedure is considered to be "free of AE". AEs are documented in the AE form, whereby distinctions in relatedness to which procedure (index phased RFA, repeated phased RFA or phased RFA re-ablation) will be made. Phased RFA procedure relatedness will also be taken from the AE form (Relatedness to Phased RFA procedure = related). The documented date of the AE will be used to set the point in time. For analysis purposes, phased RFA procedure safety will be calculated for first documented procedures (on procedure and patient level), separated for additional procedures (on procedure level) and for patients with additional procedures (on patient level).

Procedure safety will be calculated for procedures that have been carried out (number of RF applications per patient > 0) and disregarding procedure successfulness. This study objective will be calculated for the BAS and the FAS (Appendix B) for patients with signed eCRF.

Further analysis might be performed, e.g. procedure safety for using PVAC GOLD solely or not PVAC GOLD solely (using other catheter or using adjunctive devices).

**Table 7:** Procedure safety variables at AE form

AE due to definition	eCRF field: AE description	Related FID's annotated eCRF (V1.3, V1.4)
Vascular access complication	Vascular access complication 
 
• Hematoma or
 
• Arterio-venous fistula or
 
• Femoral artery pseudoaneurysm
 
	F31000010_6

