## 8.3 Statistical analyses for ancillary objectives

According to Appendix B, these analyses will be performed for the Baseline Analysis Set and Full Analysis Set. If not described otherwise, ancillary objectives will be analysed using methods of descriptive statistics (SAP chapter 8).

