## Appendix B: Analysis tables, Study objectives and Analysis sets

eCRF SEGMENTS	eCRF CHAPTERS/ANALYSIS TABLES	STUDY OBJECTIVES	ANALYSIS SETS FOR INTERIM ANALYSIS	ANALYSIS SETS FOR FINAL ANALYSIS
BASELINE	Enrolment		APS, BAS	APS, BAS, FAS, EFAS
	Indication/Admission		APS, BAS	APS, BAS, FAS, EFAS
	Demographics		BAS	BAS, FAS, EFAS
	History of CVD		BAS	BAS, FAS, EFAS
	History of AF		BAS	BAS, FAS, EFAS
	Symptoms		BAS	BAS, FAS, EFAS
	Concomitant Diseases		BAS	BAS, FAS, EFAS
	Diagnostics		BAS	BAS, FAS, EFAS
	Medications List		BAS	BAS, FAS, EFAS
	AFEQT		BAS	BAS, FAS, EFAS
	Anticoagulation (before/during first documented procedure)	ANCILLARY OBJECTIVE	BAS	BAS, FAS, EFAS
FIRST DOCUMENTED PROCEDURE	Administrative information		APS, BAS	APS, BAS, FAS, EFAS
	Procedure summary information	ANCILLARY OBJECTIVE	BAS	BAS, FAS, EFAS
	Consumables		BAS	BAS, FAS, EFAS
	PVI confirmation		BAS	BAS, FAS, EFAS
	Hospital discharge		APS, BAS	APS, BAS, FAS, EFAS
	Medication list at discharge		BAS	BAS, FAS, EFAS
ADDITIONAL PROCEDURE(S)	Administrative information		-	BAS, FAS, EFAS
	Procedure summary information	ANCILLARY OBJECTIVE	-	BAS, FAS, EFAS
	Consumables		-	BAS, FAS, EFAS
	PVI confirmation		-	BAS, FAS, EFAS
STUDY EXIT	Study exit		APS, BAS	APS, BAS, FAS, EFAS
AE	Administrative Information/Adverse Event	ADDITIONAL OBJECTIVE	-	BAS, FAS, EFAS
	Relatedness of the AE		-	BAS, FAS, EFAS
	Description of AE/AEAC		-	BAS, FAS, EFAS
GENERAL FU	Administrative Information		-	BAS, FAS, EFAS
	History of Arrhythmias since the last visit		-	BAS, FAS, EFAS

	Diagnostics		-	BAS, FAS, EFAS
	Symptoms		-	BAS, FAS, EFAS
	Hospitalizations		-	BAS, FAS, EFAS
	Medication List		-	BAS, FAS, EFAS
12MFU VISIT / 12MFU BY PHONE	Administrative Information		-	BAS, FAS, EFAS
	History of Arrhythmias since the last visit	MAIN OBJECTIVE	-	BAS, FAS, EFAS
	Diagnostics		-	BAS, FAS, EFAS
	Symptoms		-	BAS, FAS, EFAS
	Hospitalizations		-	BAS, FAS, EFAS
	Medication List		-	BAS, FAS, EFAS
	AFEQT	ANCILLARY OBJECTIVE	-	BAS, FAS, EFAS

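### The SAP admits to its Baseline Analysis Set only patients with PVAC GOLD opened and a PV application, a narrower group than the Phased RFA patients the protocol sets out to describe

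*SAP*

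**What the plan says.** **Who the protocol studies.** Protocol 3.2 asks for AF, a scheduled Phased RFA procedure, consent and age 18 or over. No particular catheter is required. Table 3-1 lists PVAC GOLD, MAAC, MASC, T-VAC and the phased-out PVAC as parts of the system, and 3.3 allows newer versions. Protocol 4.1 analyses all enrolled eligible patients, and 7.2 adds that "Information about all Phased RFA attempts will be used for the analysis". For persistent AF, the rationale in 4.4.3 is "to evaluate which tools and consumables participating centers use in persistent and long standing persistent AF".

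**Who the SAP analyses.** Among the entry conditions for the Baseline Analysis Set (BAS) in SAP 4.2 is "PVAC GOLD catheter used (opened), number of PV applications > 0". The Full Analysis Set (FAS) "consists of all patients of the BAS and thereof patients with a valid 12MFU form", and the Extended Full Analysis Set (EFAS) is a subset of the FAS. On use of the BAS, SAP 4.2 states: "The final analysis includes the additional objective (SAP chapter 8.2) and ancillary objectives (SAP chapter 8.3), where the BAS will be applied". SAP 8.3 says of the ancillary objectives that "these analyses will be performed for the Baseline Analysis Set and Full Analysis Set".

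**A different criterion elsewhere in the SAP.** Section 8.2.1 reads "Procedure safety will be calculated for procedures that have been carried out (number of RF applications per patient > 0". Sections 8.3.1 and 8.3.2 also count RF applications, not PV applications.

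**The concern.** An analysis set meant to describe how a multi-catheter system is used should not require use of one particular catheter. Under SAP 4.2, two kinds of patient can receive Phased RFA and still leave every set that carries procedure data:

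- patients treated with another Phased RFA catheter, with PVAC GOLD never opened;
- patients with no PV application, for example someone with an earlier ablation whose veins are still isolated and who is treated only elsewhere in the atrium. Previous ablation is no bar to entry and is an Appendix C subgroup.

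Three results are at stake. The catheter description in persistent AF is confined to PVAC GOLD users. The safety denominator for the system loses treated patients, along with any events they had. One predefined subgroup contrast becomes empty. Protocol 3.3 describes MAAC and MASC as relevant particularly to persistent AF, which is the population of SAP 8.3.4.

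**Working it through.** The plan gives no figure on this point, so there is none to reproduce. The check is set logic, followed by an illustration of size.

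**1. Which set carries which table (SAP Appendix B, final analysis)**

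| Table | All-Documented Patient Set (APS) | BAS, FAS, EFAS |
|---|---|---|
| "Indication/Admission" (AF type) | yes | yes |
| Procedure summary | no | yes |
| Consumables | no | yes |
| PVI confirmation | no | yes |
| Adverse events | no | yes |

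The APS is the only set without the PVAC GOLD condition, and it never carries the catheter, procedure or adverse-event tables. AF type is available without the restriction, but catheter use by AF type is not.

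**2. Consequence for SAP 8.3.4 and Consumables.** I read the SAP 4.2 condition as applying to the first documented procedure; the text does not say so outright. Every BAS patient then has PVAC GOLD opened at that procedure, so PVAC GOLD use is 100% by definition. Additional procedures in BAS patients are not bound by the condition and can show other catheters.

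**3. Consequence for Appendix C.** The subgroup *PVAC GOLD solely* requires PVAC GOLD and one catheter in total. The subgroup *Phased RFA catheter solely* requires any Phased RFA catheter and one in total. Both exclude adjunctive devices and are drawn from the FAS and EFAS. If PVAC GOLD was opened and only one catheter was used, that catheter was PVAC GOLD. The two subgroups therefore contain the same patients.

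**4. Two application criteria.** SAP 4.2 asks for PV applications > 0. SAP 8.2.1, 8.3.1 and 8.3.2 ask for RF applications per patient > 0. If these are different counts, a patient can qualify as a procedure carried out under 8.2.1 and still be absent from the set on which 8.2.1 is run.

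**5. Illustrative size for the single-catheter share.** Let S be the true share of persistent-AF Phased RFA patients treated with PVAC GOLD alone. Let q be the share excluded by SAP 4.2, and assume that none of those excluded used PVAC GOLD alone. The numerator is unchanged and the denominator shrinks, so the reported share is S/(1-q). Neither S nor q is in the documents. Taking S = 60%:

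| q (assumed) | Reported share | True PVAC GOLD use, if every excluded patient lacked it | Reported PVAC GOLD use |
|---|---|---|---|
| 1% | 0.60/0.99 = 60.6% | 99% | 100% |
| 2% | 0.60/0.98 = 61.2% | 98% | 100% |
| 5% | 0.60/0.95 = 63.2% | 95% | 100% |
| 10% | 0.60/0.90 = 66.7% | 90% | 100% |
| 20% | 0.60/0.80 = 75.0% | 80% | 100% |

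An any-catheter set with RF applications > 0 would report 60% in each row, provided all excluded patients had RF energy applied.

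**6. Safety.** The system-wide rate is (1-q) times the BAS rate plus q times the rate in excluded patients. The documents give neither q nor the second rate, so neither the size nor the direction of the shift can be stated.

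**The case against.** The case for leaving the rule alone has real weight.

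- **PVAC GOLD is a stated focus.** Protocol 1 speaks of the indications for PVAC GOLD ablation, and 4.4.1 says its clinical effectiveness has yet to be estimated. A single-catheter share among patients who had PVAC GOLD and vein applications is a legitimate quantity with a different denominator. This stands, but it supports a subgroup rather than an entry condition for describing the system.
- **No listed endpoint is PVAC GOLD versus no PVAC GOLD.** The Protocol 4.4.3 endpoints are the split of AF type and whether substrate modification was added to PVI. The sentence on tools and consumables is rationale. This also stands: a reader might infer that the plan selects on its own endpoint, and the documents do not support that. However, catheters used is the first parameter of interest in SAP 8.3.4, and that description is truncated.
- **The two application counts may be one field.** The application counts in SAP Table 3 appear to be per vein, and the eCRF is not available here. The mismatch in wording is certain; whether it changes who is counted is not.
- **Exclusions will be visible.** SAP 6.1 plans an overview of reasons for exclusion, including the BAS criteria. That would show how many were lost, but it does not provide for their catheters, AF type or adverse events.
- **The numbers may be small.** PVAC is phased out, MAAC and MASC are called secondary catheters, and PVI is described as the cornerstone of therapy. Nothing in the documents contradicts this.

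**Conclusion.** The point holds as a mismatch between the SAP's entry rule and the protocol's population. It also conflicts with the SAP's own RF-application criterion and with Appendix C. The rule makes the catheter description and the safety denominator conditional on use of one catheter. SAP 4.2 gives no reason for this, and the version history records only that analysis-set definitions changed.

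Two stronger readings should be resisted:

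- A reader might infer that all Phased RFA treatment outside the veins drops out. It does not. SAP Table 12 tabulates non-PVI lesions and their location, and Appendix C keeps subgroups with PVAC GOLD plus MAAC, MASC or other catheters. Only patients without PVAC GOLD, or with no PV application, are lost.
- A reader might infer that the 12-month success rate is materially biased. SAP 8.1.1 separately requires a first procedure confirmed successful by PVI, so the effect there is limited whatever SAP 4.2 says.

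The subgroup collapse and the 100% PVAC GOLD use follow from the definitions, given that the condition applies to the first documented procedure. The inflation of a single-catheter share by 1/(1-q) is a factor of 1.01 at q = 1%, 1.05 at 5% and 1.11 at 10%. Those values of q are assumptions, and the true effect may be small. The change is worth making because it is cheap and restores agreement with the protocol, not because a large bias has been shown.

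**What to change.** In SAP 4.2, replace the PVAC GOLD and PV-application condition by: any Phased RFA catheter used and number of RF applications > 0. This matches SAP 8.2.1, 8.3.1 and 8.3.2. Define the application count once, by eCRF field, and state whether PV applications and RF applications are the same variable and which procedure the condition refers to.

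Run safety (8.2), the consumables part of 8.3.2, and 8.3.4 on this set. Keep PVAC GOLD used with PV applications > 0 as the filter for vein-level acute success and as a named subgroup, so that no planned PVAC GOLD result is lost.

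The cost is SAP wording and one changed filter, and the set becomes slightly more heterogeneous. One limit remains. Attempts where a catheter was opened but no energy was delivered would still be outside the set, although Protocol 7.2 asks sites to keep such patients enrolled for 30 days to capture adverse events. They should at least be counted in the SAP 6.1 overview and their adverse events listed.

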### 4.3 Full Analysis Set

The *Full Analysis Set* (FAS) consists of all patients of the BAS and thereof patients with a valid 12MFU form of 12 months visit or 12 months telephone interview. The rules for valid 12MFU form are described in the chapter 7.2.3.

A documented 12MFU form includes at least:

- Date of the visit/FU and
- Vital status and
- Signed eCRF 12MFU visit or 12MFU by phone form

The FAS will be used to analyse the main objective (SAP chapter 8.1), additional objective (SAP chapter 8.2) and ancillary objectives (SAP chapter 8.3). The FAS will be analysed at the end of this study.

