4.1 Registry Population

Data from all patients who are enrolled in the study (patients who meet the eligibility criteria and have signed the PIC/PDRF) will be included in the analysis. If a patient exits from the study, data collected prior to the study withdrawal will be included in the analysis.

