## 8.1 Statistical analyses for the main objective

### 8.1.1 Estimate Phased RFA 12 month success rate

Success rate estimated as the time to first AF re-occurrence event from the first documented procedure. Data about AF events will be collected since the first documented procedure, including 90 days of the "blanking period" and closes at 12 months FU. If no AF events occur during the follow-up period (considering the "blanking period") up to 12 (+2) months, the case is considered to be "event-free". Calculations will be done for exact 12 months (351 days) after first documented procedure.

Main objective will be calculated for the BAS, FAS and EFAS (see chapter 4 and Appendix B). A successful first documented procedure (successfulness by PVI confirmation) is the basis to calculate the main objective. Patients with a procedure during the "blanking

---

 in the service agreement #2 refers to the final report, which is one and the same document for this study

period" of 90 days after first documented procedure will be excluded from main objective calculations.

Predefined AF re-occurrence definition from CIP Version 2.0 will not be applied to calculate the main objective. Further analysis might be used to estimate Phased RFA success rate considering (re-)occurring left Afl events.

AF re-occurrence event defined as:

- AF pharmacological and/or electrical CV
- AF more the 30 sec on ECG/EGM
- AF less than 30 sec in combination with AF symptoms
- Re-ablations for AF

For this analysis adjudicated AE data and coded AE data (free text fields) will be used. AF re-occurrence event rate will be estimated with and without the use of antiarrhythmic drugs at time of the 12 month follow-up. AF re-occurrence rates will be calculated for patients from BAS and FAS (Appendix B) which need to have a signed 12 month FU / 12 month FU by phone form by definition. AF re-occurrence is defined as the first event of AF re-occurrence event and their related date information based on the following eCRF forms and data fields:

**Table 4:** Main objective variables at 12MFU / General FU form

eCRF field	Related date field	Related FID's annotated eCRF (V1.3, V1.4)
Reason for visit: AF re-occurrence	Date of visit	F11000050 F11000010
Re-ablation reason: Due to AF- occurrence	Date of visit	F11000070 F11000010
History of arrhythmias since last visit: AF	Date of first occur- rence	F12000012 F12000050

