## 8.8 Graphical analysis

Graphical analysis will be provided for final analysis. The graphs will be created using SAS. Predefined graphical analysis will be done for the following topics and strata. Additional graphical analyses can be carried out after database closure.

**Table 13:** Predefined graphical analysis

Target variable	Analysis method	Patients set or strata
Main objective:  AF re-occurrence by study definition during 12 months  Additional analysis: AF re-occurrence with and without considering the "blanking period" of 90 days  AF re-occurrence up to 14 month (end of FU period) after first documented procedure	Kaplan-Meier estimation (time-to-first-event)	
 
• BAS, FAS, EFAS
 
• AF type
 

Additional objective:  Phased RFA procedure safety	Kaplan-Meier estimation (time-to-first-event)	
 
• FAS
 
• Reason for ablation: index, repeated, re-ablation, left Afl
 

Anticoagulation medication before /during/ after/ at 12months FU	Graphical (stacked) bar analysis	
 
• FAS, EFAS
 
• LAAO implantation
 

Analysis of procedure time by 
 
• Site
 
• Operator
 
	Box-whisker plots	
 
• FAS, EFAS
 

Correlation between Anticoagulation and 
 
• INR
 
• ACT
 
• Stroke
 
	Suitable correlation methods	
 
• FAS
 

Correlation between AF re-occurrence and 
 
• BMI
 
• Age
 
	Suitable correlation methods	
 
• BAS, FAS, EFAS
 

COX regression analysis (SAP chapter 8.1.2)	Forest plot (for HR + CI)	
 
• FAS, EFAS
 

Analysis of DAP - by site	Box-whisker plots	
 
• BAS
 

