## Appendix D: Analysis of comparison groups

Predefined comparison groups (V1.0)

Comparison description	Analysis set, additional inclusion or exclusion criteria	Tables and scope for analysis	At time of Interim analysis	At time of Final analysis
Age <65, 65-74, ≥75	FAS, EFAS incl.: Age available excl.: ---	Baseline First documented procedure Additional procedure GFU 12MFU	-	X
Body Mass Index <18.5, 18.5 to <25, 25 to <30, ≥30	FAS, EFAS incl.: BMI available excl.: ---	Baseline First documented procedure Additional procedure GFU 12MFU	-	X
EHRA AF symptoms (at admission during the last 12 months) None, Yes – I "No", II "Mild", III "Severe", IV "Disabling"	FAS, EFAS incl.: AF symptoms available excl.: ---	Baseline First documented procedure Additional procedure GFU 12MFU	-	X
Gender Males, Females	BAS, FAS, EFAS incl.: Gender available excl.: ---	Baseline First documented procedure Additional procedure GFU 12MFU	X	X
First documented procedure Regular case, Training case	BAS, FAS, EFAS incl.: Regular or training case available excl.: ---	First documented procedure Additional procedure GFU 12MFU	X	X
Discharge after First documented procedure Patient discharged home, Transferred to another hospital, Death	FAS, EFAS incl.: Discharge available excl.: ---	First documented procedure Additional procedure GFU 12MFU	-	X
Adverse events Patients with AE during 12 months, Patients w/o AE during 12 months	FAS, EFAS incl.: Adjudicated events available excl.: ---	First documented procedure Additional procedure GFU 12MFU	-	X
Re-occurrence of AF Patients with re-occurrence AF, Patients w/o re-occurrence AF during 12 months	FAS, EFAS incl.: --- excl.: ---	Baseline First documented procedure GFU 12MFU	-	X
First documented procedure Phased RFA <40 min of fluoroscopy time vs. ≥ 40 min of fluoroscopy time	BAS, FAS, EFAS incl.: Fluoroscopy time available excl.: ---	First documented procedure Additional procedure GFU 12MFU	X	X
First documented procedure	BAS, FAS, EFAS	First documented procedure Additional procedure GFU 12MFU	X	X

General time of the procedure time <100 min vs. >=100 min	incl.: Total procedure time available excl.: ---			
Patients with more than 5 GFU vs. all other patients	BAS, FAS, EFAS incl.: --- excl.: ---	Baseline GFU 12MFU	-	X
Patients lost to 12MFU vs. not lost to 12MFU (according SAP chapter7)	BAS incl.: --- excl.: ---	Baseline GFU 12MFU	-	X
Analysis of missed data	BAS incl.: --- excl.: ---	Full tables set	-	X

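### The SAP ties the 12-month success rate to patients with a completed 12-month form, contradicts itself on whether the baseline set escapes that condition, and names no primary set

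*SAP*

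**What the plan says.** **Sets.** By SAP 4.3 the FAS is a set that "consists of all patients of the BAS and thereof patients with a valid 12MFU form of 12 months visit or 12 months telephone interview"; that form must carry a date, vital status and a signature. SAP 4.3 then assigns the objectives: "The FAS will be used to analyse the main objective (SAP chapter 8.1), additional objective (SAP chapter 8.2) and ancillary objectives (SAP chapter 8.3"). By contrast, the BAS in SAP 4.2 requires a started procedure and baseline documentation, but no 12-month form. Its stated use is: "The final analysis includes the additional objective (SAP chapter 8.2) and ancillary objectives (SAP chapter 8.3), where the BAS will be applied". The main objective is not in that sentence.

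**Main objective.** SAP 8.1.1 says the main objective is calculated for the BAS, FAS and EFAS (the Extended FAS, a subset of the FAS). Table 13 and Appendix B agree. SAP 8.1.1 then says recurrence rates are for BAS and FAS patients "which need to have a signed 12 month FU / 12 month FU by phone form by definition".

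**Early exit.** Protocol 4.1: "If a patient exits from the study, data collected prior to the study withdrawal will be included in the analysis". Protocol 4.4.1 and SAP 8.1.2 both censor event-free patients at the last study contact.

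**Safety.** SAP 4.2, 8.2.1 and Appendix B put safety in the BAS (8.2.1 and Appendix B in the FAS as well). In Table 13 (SAP 8.8) the Kaplan-Meier row for "Phased RFA procedure safety" lists the FAS alone.

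**Deaths.** Protocol 7.2 asks for the Exit form in addition to the General FU form when the "PI receives information about the patient’s death". Appendix D nevertheless plans a discharge comparison with the groups "Patient discharged home, Transferred to another hospital, Death", in the FAS and EFAS only.

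**The concern.** FAS membership is decided about a year after the procedure and can depend on what happened in between: recurrence, re-ablation elsewhere, withdrawal or death. A patient with documented AF at month 5 who then leaves the registry has an observed endpoint event, yet is not in the FAS.

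Kaplan-Meier estimation already deals with early exit by censoring. Requiring completion on top of that adds selection and removes known events. If the clause in SAP 8.1.1 is programmed as written, the BAS run becomes a completer analysis too, and no estimate covers all treated patients. Even if it is not, one main objective yields three success rates with nothing to say which is the headline.

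**Working it through.** **1. Which outputs have a BAS version**

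| Output | Sets named | BAS version? |
|---|---|---|
| Main objective, SAP 4.2 and 4.3 | FAS (4.3); not listed for the BAS (4.2) | No |
| Main objective, SAP 8.1.1, Table 13, Appendix B | BAS, FAS, EFAS | Yes, unless the signed-form clause is applied |
| Safety rates, SAP 4.2, 8.2.1, Appendix B | BAS; also FAS (8.2.1, Appendix B) and EFAS (Appendix B) | Yes |
| Safety Kaplan-Meier graph, Table 13 | FAS | No |
| Cox models for recurrence, SAP 8.1.2; forest plots, Table 13 | FAS; FAS and EFAS | No |
| Appendix C subgroups (other than the lost-to-follow-up group) | FAS, EFAS | No, although Table 13 lists AF type as a stratum beside the BAS |
| Appendix D comparisons by AE and by discharge status | FAS, EFAS | No |

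**2. What censoring can do in the FAS.** The 12-month window opens at about day 351 (protocol Table 7-2, SAP 7.2.3), and SAP 8.1.1 reads the estimate at day 351. Event-free FAS members have in general already reached the readout. Censoring at last contact therefore has almost nothing to act on, and the Kaplan-Meier estimate is close to a simple completer proportion.

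**3. How many patients may be affected.** Protocol 4.3 plans 800 evaluable patients plus 200 drop-outs: 800 × 1.25 = 1000, which reproduces the stated enrolment. That is 200/1000 = 20% of those enrolled, or 25% as the plan words it. It is total drop-out, so the loss from BAS to FAS may be smaller, because patients with no procedure started are already outside the BAS.

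**4. Size, by hand.** Let S be true 12-month success and d the extra fraction of recurrent patients who leave without a 12-month form. Loss unrelated to recurrence cancels, so

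FAS success = S / [S + (1 − S)(1 − d)].

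Take S = 0.74, the reference efficacy in protocol 4.4.1 (average follow-up 10 months, used here only for illustration), and assume values of d:

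- d = 0: 74.0%
- d = 0.10: 0.74/0.974 = 76.0%
- d = 0.20: 0.74/0.948 = 78.1%
- d = 0.30: 0.74/0.922 = 80.3%

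**5. Size, by simulation.** This used 400,000 patients and a constant recurrence hazard after day 90, set to 74% freedom at day 351. The exit hazard after recurrence is k times the hazard before it, tuned so that 20% or 25% lack the form. Estimates are Kaplan-Meier at day 351. The values of k are assumptions.

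| k | FAS, 20% lost | FAS − BAS | FAS, 25% lost | FAS − BAS |
|---|---|---|---|---|
| 0.5 | 73.0% | −0.9 | 72.6% | −1.3 |
| 1 | 74.0% | +0.1 | 73.9% | 0.0 |
| 2 | 75.5% | +1.6 | 75.9% | +2.0 |
| 3 | 76.8% | +2.8 | 77.5% | +3.6 |
| 5 | 78.6% | +4.7 | 79.8% | +5.9 |

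The BAS estimate is 73.9-74.0% throughout. The FAS discards 11-66 observed recurrences per 1000 patients (20% lost) or 14-79 (25% lost). At k = 1, where there is no net bias, it still discards 21 or 25.

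**6. Yardstick.** The plan states a precision of ±3.8 points. Its own inputs give 1.96 × √(1.2 × 0.2 × 0.8 / 800) = 3.04 points. Only k = 5 exceeds 3.8. With 25% lost, k = 3 also exceeds 3.04.

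**7. Safety graph.** Take 39 complications per 1000 (the 3.9% survey rate in protocol 4.4.2), of which f are fatal and absent from the FAS. Let m be the fraction without a form, and let non-fatal cases lack it r times as often. The FAS rate is (39 − f)(1 − rm) / [1000(1 − m)]. For f = 1 to 5:

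- r = 1: 3.8% to 3.4%
- r = 2, m = 0.20: 2.9% to 2.6%
- r = 2, m = 0.25: 2.5% to 2.3%

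The values of f and r are assumptions.

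**The case against.** Four stronger readings are tempting, and the documents do not support them.

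- **That the main objective is run only in completers.** SAP 8.1.1, Table 13 and Appendix B also list the BAS. The signed-form clause may be loose wording: only the FAS has the form by definition, and if the clause governed both sets, running both would be pointless. That reading is plausible, but the text does not settle it and a programmer could follow either.
- **That fatal complications vanish from the safety rates.** They do not. Safety is assigned to the BAS in three places, SAP 8.2.2 does not limit the rates to the FAS, and protocol 11.1.1 requires an Adverse Event form for a related death. The gap is the Table 13 graph and the FAS-only comparisons.
- **That deaths in the FAS are zero by construction.** The 12-month form has a vital-status field, and nothing bars a death from being entered there. An early death already on the Exit form would normally be absent, but the documents do not establish that it must be.
- **That the success rate is necessarily inflated.** The exit patterns are assumed. The difference is nil if exit is unrelated to recurrence and reverses if patients who are well skip the form. Follow-up is unscheduled and visits may be prompted by recurrence (SAP 3.1), so censoring in the BAS may itself be informative. The simulation assumes that away.

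The SAP also plans drop-out percentages, reasons, and comparisons of patients lost and not lost to the 12-month contact (SAP 7, 8, Appendices C and D), and this is a descriptive registry with no confirmatory hypothesis. Those checks describe the selection; they do not return discarded events to the FAS estimates. These points limit the severity but do not remove the contradiction.

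**Conclusion.** The concern holds in a limited form. SAP 4.2, 4.3 and 8.1.1 disagree on which patients carry the main objective, no set is primary, and the set most directly assigned to it discards observed events that protocol 4.1 says are included. The safety rates are adequately placed in the BAS; the safety graph, the recurrence Cox models, the Appendix C reports and the Appendix D AE and discharge-status comparisons are not.

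In the simulated scenarios the FAS success estimate departs from the BAS by about −1 to +6 points. This rests on 74% true success, 20-25% of patients without a form, and exit hazards after recurrence of 0.5 to 5 times those before it. It is an illustration of range, not a prediction. The BAS figure is the better primary estimate because it keeps every observed event, not because it is guaranteed unbiased. The point should be fixed.

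**What to change.** - SAP 4.2, 4.3 and 8.1.1: name the BAS as the primary set for the main objective.
- SAP 8.1.1: delete the signed-form clause, so that the last-contact censoring already in SAP 8.1.2 operates.
- Keep the FAS as a sensitivity analysis, labelled as completers only.
- Table 13: add the BAS to the safety row. SAP 8.1.2: add it to the recurrence Cox models, which cover the Appendix C subgroups. Appendix D: add it to the AE and discharge-status comparisons.
- State whether a death known before the 12-month window generates a 12-month form, so that FAS membership is unambiguous.

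The other restrictions in SAP 8.1.1 (a successful first procedure, no further procedure in the blanking period) are a separate matter and are not changed here.

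The cost is SAP wording and a change of analysis-set flag, with no new data. The reported success rate may become slightly less favourable.
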